3.1.3.5 Assumptions for statistical test

The Kaplan-Meier analysis method assumes that censored individuals have the same prospect of survival as those who continue to be followed. Additionally, it is assumed that survival prospects are the same for early as for late recruits to the study.

4 GENERAL STATISTICAL METHODS

4.1 Analysis Sets

All patients that are successfully implanted with the ACUITY Spiral Lead and still actively followed in the study at 45 days post implant will be included in the Primary endpoint analysis. Subjects without an endpoint event who die/withdraw prior to completing 5 years of follow-up will be censored at the death or withdrawal date.

All subjects with an attempted or implanted ACUITY Spiral Lead will be included in the modified analysis as requested by FDA (see section 5.3 for details of this additional analysis).

4.2 Control of Systematic Error/Bias

The LSR of ACUITY Spiral Study is a post-approval clinical study and as such study subjects will essentially include "all-comers" who meet enrollment criteria. Study Investigators are expected to approach all potentially eligible study subjects who have been (within 29 calendar days post implant window), or will be, implanted with the ACUITY Spiral Lead at the investigational center for enrollment into this study until the enrollment ceiling is reached.

5 ADDITIONAL DATA ANALYSES

5.1 Progress Reports

Progress reports to the FDA will be provided by the sponsor every six months. Data for these reports will come from two sources defined as 'Database' and 'ADAM'. The Database is the data repository for the data entered into the electronic data capture system (eDC). ADAM is the data repository that stores data from the LATITUDE remote monitoring system. With protocol revision AC, the use of the LATITUDE remote monitoring system is optional. For those subjects that are on LATITUDE, data from the in-clinic visits will automatically be transferred to BSC and retrieved for analysis via ADAM. For subjects not on LATITUDE (or for whom LATITUDE is not working properly), data from in-clinic visits will be entered into eDC and retrieved for analysis via the Database.

Data in the 6-month progress reports includes, but is not limited to:

- Summary of enrollment and lead status
- Kaplan-Meier plot of time to first endpoint defined chronic ACUITY Spiral Lead-related complication
- Summary of trend analysis (not provided by Biostatistician)
- Summary of LV-lead related adverse events

5.2 Interim Analyses

While the primary endpoint will be analyzed at 5 years, in order to monitor the safety of the study during the enrollment and follow-up phases, BSC has agreed to provide an estimate of the chronic complication-free rate to the FDA in each bi-annual (every 6 months) progress reports. This will include a Kaplan-Meier plot and a table of all adverse events and whether they were adjudicated as counting towards the endpoint or not.

Currently no formal interim analyses are planned for the purpose of stopping this study early for futility, as this is an FDA mandated post market study. However, we will be monitoring the attrition rate and enrollment rates to be able to adequately report to FDA when we believe the study will be completed.

5.3 FDA Requested Modified Complication-Free Rate

Per FDA feedback received on the 30-month Interim Study Status Report (P010012/R028) and subsequent amendment (A001), an additional Kaplan-Meier curve and table will be presented in each 6-month report. This analysis provides data in the form of a modified composite endpoint identical to the analyses provided for the primary endpoint with the following modifications:

- a) Chronic events occurring 30 days or greater post-implant
- b) Dislodgements occurring 30 or more days post-implant that result in permanent loss of therapy, invasive intervention, injury, or death

- c) Elevated LV pacing threshold, intermittent LV capture, and no capture of LV lead occurring 30 or more days post-implant that result in permanent loss of therapy, invasive intervention, injury, or death
- d) Diaphragmatic/muscle stimulation occurring 30 or more days post-implant that result in permanent loss of therapy, invasive intervention, injury, or death
- e) All LV lead-related perforations

Prior to each 6-month report, the study team will meet to review all new/changed adverse events since the last report to determine inclusion into the modified analysis. The study Biostatistician is responsible for keeping a spreadsheet with all adverse events and the status of inclusion into the modified endpoint.

5.4 Pooling Analysis

If required, center-to-center heterogeneity will be assessed for the primary endpoint by performing a random effects logistic regression analysis. Centers will be deemed to be heterogeneous if the variance of the random center effect is found to significantly differ from zero. A significance level of 10% will be used for this test.

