4.1.1.3. Sample Size

Based on the calculations below, the sample size for this registry is approximately 1700 patients implanted with the ACUITY Spiral Lead.

A binomial exact calculation with the parameters in Table 4 was used to determine the approximate sample size necessary to detect a clinically meaningful change with 80% power and a one-sided α -level of 0.05.

Table 2: Sample Size Parameters and Justification

Primary Endpoint	N	P	Δ	95% Confidence Boundary	Justification
Chronic LV lead-related complications	1000	94.5%	2.0	92.5%	Prospectively defined based on predicate data from EASYTRAK lead [†] . 95% confidence boundary is clinically acceptable.

Attrition is expected due to death, withdrawal, and loss-to-follow-up. Assuming an annual attrition rate of 10%, a minimum of 1700 patients implanted with the ACUITY Spiral Lead is necessary to obtain 5-year follow-up data on approximately 1000 patients.

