3.1.2 Sample Size

Based on the calculations below, the sample size for this registry is approximately 1700 patients implanted with the ACUITY Spiral Lead with a successful LATITUDE data transmission. An exact binomial calculation with the parameters in Table 3-1: **Sample Size Parameters and Justification** was used to determine the approximate sample size necessary to detect a clinically meaningful change with 80% power and a one-sided α -level of 0.05. An annual attrition rate of 10% is assumed over the five-year follow-up.

Table 3-1: Sample Size Parameters and Justification

Primary Endpoint	N	P	Δ	95% Confidence Boundary	Justification
Chronic LV lead-related complications	1000	94.5%	2.0	92.5%	Prospectively defined based on predicate data from EASYTRAK lead*. 95% confidence boundary is clinically acceptable.

*The EASYTRAK lead was studied as part of the CONTAK CD/EASYTRAK Post Approval Study (PMA P010012). Mean implant duration was 26±13 months, with a cumulative implant duration of over 25,000 patient months. The 3 year chronic lead-related complication free rate was 97.9% using Kaplan-Meier methods. Assuming a continued 1.7% annual rate (consistent with observed year to year changes in rates from previous pre-market LV lead studies) from years 3 to 5 would result in an estimated 94.5% chronic complication free-rate at 5 years for the EASYTRAK LV lead.

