3.1.3 Statistical Methods

3.1.3.1 Overview

When the final study subject reaches five (5) years of follow-up, the primary analysis will be performed based on the Kaplan-Meier method for the estimation of the five (5) year chronic lead-related complication-free rate, including the lower one-sided 95% confidence interval. The censoring mechanism of the Kaplan-Meier analysis incorporates all available data on study subjects, including those that withdrew or were lost-to-follow-up.

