3.1.3.4 Tests to be performed

The primary endpoint will evaluate the 5-year chronic lead-related complication-free rate, calculated using Kaplan-Meier (product-limit) methods. The Kaplan-Meier analysis will begin at the time of implant for each study subject. The null hypothesis will be rejected in favor of the alternative if the lower one-sided 95% confidence limit for the chronic lead-related complication-free rate is greater than 92.5%. This analysis will be performed after the last subject has completed 5 years of follow-up. The 5-year survival estimate will be calculated using product-limit survival estimates as follows:

Let $t_1 < t_2 < \dots < t_D$ represent the distinct event times. For each $i = 1, \dots, D$, let n_i be the number of surviving units (the size of the risk set) just prior to t_i . Let d_i be the number of units that fail at t_i , and let $s_i = n_i - d_i$.

The Kaplan-Meier (product-limit) estimate of the survivor function at t_i is the

$$\text{cumulative product } \hat{S}(t_i) = \prod_{j=1}^i \left(1 - \frac{d_j}{n_j}\right)$$

All the estimators are defined to be right continuous. The corresponding estimate of the standard error is computed using Greenwood's formula (Kalbfleisch and Prentice; 1980) as

$$\hat{\sigma}(\hat{S}(t_i)) = \hat{S}(t_i) \sqrt{\sum_{j=1}^i \frac{d_j}{n_j s_j}}$$

The lower 95% confidence bound at t_i is calculated in SAS as follows:

$$100 * (\hat{S}(t_i) - \text{probit}(0.95) * \hat{\sigma}(\hat{S}(t_i)))$$

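### SAP 5.4 checks center heterogeneity of a censored five-year endpoint with a logistic model that names no follow-up time; a time-to-event model with a random center effect would be a near-free improvement

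*SAP*

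**What the plan says.** The primary analysis is a survival analysis. SAP 3.1.3.4: "The primary endpoint will evaluate the 5-year chronic lead-related complication-free rate, calculated using Kaplan-Meier (product-limit) methods". SAP 4.1 sets the censoring rule: "Subjects without an endpoint event who die/withdraw prior to completing 5 years of follow-up will be censored at the death or withdrawal date". SAP 3.1.3.1 presents this as the way partial follow-up is used: "The censoring mechanism of the Kaplan-Meier analysis incorporates all available data on study subjects, including those that withdrew or were lost-to-follow-up".

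Substantial loss is planned for. SAP 3.1.2: "An annual attrition rate of 10% is assumed over the five-year follow-up". Protocol 4.1.1.3 concludes that "a minimum of 1700 patients implanted with the ACUITY Spiral Lead is necessary to obtain 5-year follow-up data on approximately 1000 patients".

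For the same endpoint, SAP 5.4 says that, if required, "center-to-center heterogeneity will be assessed for the primary endpoint by performing a random effects logistic regression analysis". The criterion is "Centers will be deemed to be heterogeneous if the variance of the random center effect is found to significantly differ from zero", and "A significance level of 10% will be used for this test". Section 5.4 does not say:
- how a patient censored before five years enters the model;
- whether follow-up time is used;
- which test statistic or reference distribution applies;
- what makes the check required, or what follows from its result.

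**The concern.** An ordinary logistic model needs a yes or no for every patient. Someone who leaves at year two without an event has neither, so must be counted as event-free or left out. Both choices tie a center's event share to its attrition, and in opposite directions. The check then compares a mixture of hazard and retention, not the quantity that the Kaplan-Meier analysis estimates.

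Unequal follow-up between centers is plausible, though the documents do not quantify it. Visits follow each center's own schedule (Protocol 2.1). The sponsor may end a noncompliant investigator's participation (Protocol 10.3). Appendix B brings centers in gradually and allows last follow-up once the 1000th patient reaches five years, which could shorten follow-up at late-starting centers.

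At stake is how a center comparison would be read: a false signal from uneven retention, or a real difference in lead performance that is missed.

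**Working it through.** **Inputs from the documents.** Expected five-year complication-free rate 94.5%, boundary 92.5%, N = 1000 and 10% annual attrition (SAP 3.1.2); 1700 implanted (Protocol 4.1.1.3); at most 150 centers (Protocol 3.3); 10% level (SAP 5.4).

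**Assumptions.** Constant event hazard, exponential attrition, time counted from implant, and center attrition split 5%/15% or 2%/25%. The documents give no between-center spread.

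**1. The plan's own figures.** Exact binomial with n = 1000, 92.5% against 94.5%: success needs at least 939 complication-free patients, with alpha 0.0493 and power 81.7%. Attrition: 1000/0.9^5 = 1694 and 1700 × 0.9^5 = 1004. Both agree with the plan. The share without five-year data is 1 − 0.9^5 = 41%.

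**2. Event share at one common hazard.** Let λ = −ln(0.945)/5 = 0.0113 per year and c = −ln(1 − annual attrition).
- Censored counted as event-free: A = λ/(λ+c) × [1 − exp(−5(λ+c))].
- Incomplete event-free patients dropped: B = A/[A + exp(−5(λ+c))].

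At 5% attrition, c = 0.0513: A = 0.1807 × (1 − 0.7312) = 4.86%, and B = 0.0486/(0.0486 + 0.7312) = 6.23%. At 15%, c = 0.1625: A = 0.0651 × (1 − 0.4193) = 3.78%, and B = 0.0378/(0.0378 + 0.4193) = 8.27%.

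| Annual attrition | True five-year rate | A | B |
|---|---|---|---|
| 2% | 5.5% | 5.23% | 5.77% |
| 5% | 5.5% | 4.86% | 6.23% |
| 10% | 5.5% | 4.29% | 7.13% |
| 15% | 5.5% | 3.78% | 8.27% |
| 25% | 5.5% | 2.94% | 11.57% |

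**3. Information available.** Expected events at 10% attrition: 1700 × 4.29% = 73, or about 0.5 per center with 150 centers.

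**4. Effect on the test.** Simulation with 1000 runs, 1700 patients and 150 near-equal centers, half at each attrition rate. The likelihood-ratio test of the center variance used the critical value 1.64 (10% under the 50:50 mixture). The comparator is a random-intercept Poisson model with log follow-up time as offset. Entries are rejection rates; Monte Carlo error is about 1 to 1.5 points.

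| Scenario | Logistic, censored = no event | Logistic, incomplete dropped | Poisson with offset |
|---|---|---|---|
| No center effect, attrition 10% everywhere | 7.5% | 7.1% | 7.6% |
| No center effect, 5%/15% | 9.0% | 9.1% | 7.9% |
| No center effect, 2%/25% | 14.3% | 16.3% | 7.8% |
| Hazard 0.5×/2×, attrition 10% everywhere | 58.2% | 59.0% | 58.8% |
| Hazard 0.5×/2×, attrition 5%/15%, higher in worse centers | 39.2% | 87.7% | 62.5% |
| Hazard 0.5×/2×, attrition 2%/25%, higher in worse centers | 19.9% | 97.7% | 63.9% |

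In the last row the true five-year rates are 1 − 0.945^0.5 = 2.8% and 1 − 0.945^2 = 10.7%. With censored patients counted as event-free, they appear as 2.7% and 5.7%. Dropping incomplete patients exaggerates the same contrast, so the direction of the distortion depends on a coding that the SAP leaves open.

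**5. Reference distribution.** Zero is the lower limit of a variance. With no center effect, the likelihood-ratio statistic is asymptotically zero half the time and chi-square with one degree of freedom otherwise. The ordinary 10% critical value therefore gives 0.5 × 10% = 5%. The value 1.64 gives 0.5 × 20% = 10%.

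**The case against.** The check is conditional, no decision depends on it, and section 5.4 is a brief description. A discrete-time logistic model, with one record per patient and interval, would respect follow-up, so the fair charge is partly under-specification. With 73 events over up to 150 centers, no model will estimate a center variance well. All of this stands. It limits the importance of the point but does not remove it, because the SAP names a model family for binary outcomes and nothing in it supplies a discrete-time form. The assumptions in SAP 3.1.3.5 concern Kaplan-Meier only.

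A reader might infer three stronger things that the documents do not support.
- **That attrition will in practice pass for, or conceal, differences in lead performance.** No between-center spread is given. At 5%/15% the false-positive rate is about 9%, still under the nominal 10%; it exceeds 10% only at the extreme 2%/25% split. The masking figures need a fourfold hazard difference that lines up with attrition.
- **That the 10% level is not delivered.** SAP 5.4 names no reference distribution, so the chi-square point applies only if the ordinary default is used, and that error would be conservative.
- **That the registry's conclusion is at risk.** The decision rule in SAP 3.1.1 and 3.1.3.4 does not use this check.

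**Conclusion.** The point holds as a low-priority improvement. The logistic model in SAP 5.4 does not match the censored endpoint it is meant to examine. At an identical hazard, event shares differ by about 1 point (4.9% against 3.8%) or 2 points (6.2% against 8.3%) between centers with 5% and 15% annual attrition, depending on the coding. False heterogeneity stays small unless attrition differs greatly between centers. Masking arises mainly if worse-performing centers also have higher attrition and censored patients are counted as event-free. With equal attrition the two kinds of model agree (58% against 59% power).

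These sizes rest on the assumed attrition spreads, constant hazards and equal-sized centers. The simulated data also have the constant hazard that the Poisson comparator assumes.

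**What to change.** In SAP 5.4, replace the logistic model with a time-to-event model that has a random center effect: a Cox model with center frailty, or a random-intercept Poisson model with log follow-up time as offset. Use the time origin and censoring of the primary Kaplan-Meier analysis. That origin must first be reconciled, because SAP 3.1.3.2 starts the analysis at 45 days after implant and SAP 3.1.3.4 at implant. If the variance is tested by likelihood ratio, state that the 50:50 chi-square mixture is the reference. The same edit could say what makes the check required.

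The cost is a few sentences. No new data are needed, SAP 7 already allows software other than SAS, and SAP 5.5 provides for changes documented before the five-year analysis. A small downside remains: with about 73 events over up to 150 centers, any test of center variance is imprecise, and even the recommended version ran at about 8% in simulation, not 10%. The change makes the check relevant to the endpoint; it does not make it exact.

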5.5 Changes to Planned Analyses

Any changes to the planned statistical analyses made prior to performing the 5-year analyses will be documented in a Statistical Analysis Plan approved prior to performing the analyses. Changes from the planned statistical methods after the 5-year primary endpoint analysis will be documented in the clinical study report along with a reason for the deviation.

6 VALIDATION

All clinical data reports generated per this plan will be validated per 90702587, Global WI: Clinical Data Reporting Validation.

7 PROGRAMMING CONSIDERATIONS

All endpoint analyses will be performed in SAS, version 9.2 or later. In the event an analysis is required that is better suited for a statistical package other than SAS, this other package (e.g. R) will be used.
